7.2 Laboratory Tests

For both cohorts, at each time point serum golimumab measurements will be made as well as measurements of antibodies to golimumab, serum CRP and albumin. Routine biochemical measurements (CRP and albumin) will be processed in the standard NHS manner. Agreement is in place with our local reference chemistry laboratory (Viapath) for ELISA measurements of golimumab concentrations and anti-drug antibodies using a commercially available assay (LISA TRACKER, produced by Theradiag). Samples from King's College Hospital for golimumab serum concentrations and anti-drug antibody measurement will be transferred to Vipath via an established sample transfer route.

Fecal calprotectin measurements will also be taken at each study time point (i.e. weeks 6, 10 and 14 in cohort 1 and at a single point in cohort 2). The faecal calprotectin samples will be handled in the standard NHS manner, which involves transfer to the reference chemistry laboratory (via an established sample transfer route) at King's College Hospital.

8 Assessment of Efficacy

Clinical disease activity will be evaluated at each time point (weeks 6, 10 and 14) using the Simple Clinical Colitis Activity Index (SCCAI) and a recently defined two-item (stool frequency and rectal bleeding) patient reported outcome (PRO2) score. Quality of life will be assessed using the IBD-Control questionnaire.

8.1.1 Primary Efficacy Parameters

- Drug exposure to golimumab using serum trough level concentrations.
- Clinical UC disease activity using SCCAI using the following definitions:
 - Remission: SCCAI ≤ 2
 - Response: SCCAI \leq 5, with a decrease by \geq 2
 - Relapse: SCCAI \geq 5 (following a response)

8.1.2 Secondary Efficacy Parameters

UC disease activity assessments using PRO2, development of anti-drug antibodies, acute infusion reactions (allergic), fecal calprotectin, serum CRP measurements, albumin, QoL assessments using IBD-Control at each time point.

8.2 Procedures for Assessing Efficacy Parameters

For serum trough golimumab levels, anti-drug antibodies and CRP venepuncture will be carried out with 15 ml to be drawn within three days of the subsequent golimumab dose during induction therapy (cohort 1) or one week of subsequent dose during maintenance therapy (cohort 2). Clinical and biochemical disease (calprotectin) activity assessments and quality of life measurements will be collect at weeks 6, 10 and 14 in cohort 1 and week 4 in cohort 2.

9 Assessment of Safety

9.1 Specification, Timing and Recording of Safety Parameters

General safety assessments will be made as part of each assessment.

9.2 Procedures for Recording and Reporting Adverse Events

The Medicines for Human Use (Clinical Trials) Regulations 2004 and Amended Regulations 2006 gives the following definitions:

Adverse Event (AE): Any untoward medical occurrence in a subject to whom a medicinal product has been administered including occurrences which are not necessarily caused by or related to that product.

Adverse Reaction (AR): Any untoward and unintended response in a subject to an investigational medicinal product which is related to any dose administered to that subject.

Unexpected Adverse Reaction (UAR): An adverse reaction the nature and severity of which is not consistent with the information about the medicinal product in question set out in:

The summary of product characteristics (SmPC) for that product (for products with a marketing authorisation)

Serious adverse Event (SAE), Serious Adverse Reaction (SAR) or Unexpected Serious Adverse Reaction (USAR): Any adverse event, adverse reaction or unexpected adverse reaction, respectively, that

Results in death; Is life-threatening; Required hospitalisation/prolongation of existing hospitalisation; Results in persistent or significant disability or incapacity; Consists of a congenital anomaly or birth defect.

Important Medical Events (IME) & Pregnancy

Events that may not be immediately life-threatening or result in death or hospitalisation but may jeopardise the patient or may require intervention to prevent one of the other outcomes listed in the definition above should also be considered serious.

Although not a serious adverse event, any unplanned pregnancy will also be reported via the SAE reporting system.

Reporting Responsibilities

King's Health Partners Clinical Trials Office (KHP-CTO) is responsible for Pharmacovigilance (as defined in Regulation 5 of the Medicines for Human Use (Clinical Trials) Regulations 2004

All SAEs, SARs and SUSARs will be reported immediately by the Principle Investigator (and certainly no later than 24hrs) to the KHP-CTO in accordance with the current Pharmacovigilance Policy. All SAEs, SARs and SUSARs are to be reported to MSD's Drug Surveillance Department ("MSD DSD") group by the Chief Investigator, including but not limited to all initial and follow up information involving any study subject.

The KHP-CTO will report SUSARs to the regulatory authorities (MHRA, competent authorities of other EEA (European Economic Area) states in which the trial is taking place.

The Chief Investigator will report to the relevant ethics committee. Reporting timelines are as follows:

- SUSARs which are fatal or life-threatening must be reported not later than 7 days after the sponsor is first aware of the reaction. Any additional relevant information must be reported within a further 8 days.
- SUSARs that are not fatal or life-threatening must be reported within 15 days of the sponsor first becoming aware of the reaction.

The Chief Investigator and KHP-CTO will submit a Development Safety Update Report (DSUR) relating to this trial IMP, to the MHRA and REC annually.

9.2.1 Adverse events that do not require reporting

AE's will not be collected during the study period but will be managed as per the standard of care. Only injection-site reactions will be collected as AR's during the trial period. They will be managed as per the standard of care.

9.3 Treatment Stopping Rules

Because this is a non-interventional trial there won't be an interim analysis or premature termination of the study. The trial may be prematurely discontinued by the sponsor, chief investigator or regulatory authority on the basis of new safety information or for other reasons given by the regulatory authority or ethics committee.

10 Statistics

To determine a representative cut-off value for golimumab trough levels between the groups of patients stratified by disease activity/response a receiver-operator characteristics (ROC) curve will be created. A trade-off between sensitivity and specificity will be made to establish an adequate lower margin of the therapeutic golimumab range. This statistical plan was reviewed by an independent statistician at King's College London. Relationships between golimumab trough levels and patient characteristics and clinical parameters (albumin, serum CRP, formation of ADA's, fecal calprotectin and IBD-Control) will be evaluated.

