4.1. Trial Objectives

Primary Objective

Protocol

To define a week 6 golimumab trough level concentration that predicts response at week 14.

Secondary Objectives

To define golimumab trough level concentrations at weeks 6, 10 and 14 that predict response at each time point, respectively.

To define a golimumab trough threshold that is associated with remission during maintenance therapy.

Tertiary Objectives

Tertiary objectives will centre on the study of the relationship between serum golimumab trough levels and novel disease activity indices (PRO2), biochemical markers of disease activity (CRP, faecal calprotectin) and quality of life indices. The role played by anti-drug antibodies will also be investigated in relation to trough levels and disease activity.

The role played by anti-drug antibodies will be investigated in relation to golimumab trough levels and disease activity.

This study will also generate data that can be used to validate a commercially available golimumab assay as well as a novel patient reported outcome (PRO) assessment of disease activity.

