10.1 Sample Size

To achieve a power of 80%, with two-sided significance, and to detect a mean difference

in serum concentration of 2 mg/L difference a minimum sample size of 42 patients in each cohort would be required. Increasing the sample size beyond this point would achieve greater power to detect smaller differences in serum concentrations between subgroups.

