10.2 Analysis

Descriptive statistics will be used to analyze baseline characteristics. The primary variable of interest will be golimumab drug levels. Other variables will include: efficacy, gender, age, smoking status, concomitant medication, disease location, disease duration, development of anti-drug antibodies, acute infusion reactions, serum CRP, albumin, fecal calprotectin, SCCAI, PRO2, IBD-Control.

Differences between responders and non-responders will be evaluated using a t-test with the threshold for statistical significance set at 0.05. Univariate and bi-variate analysis will be used to assess factors predicting response, including serum golimumab levels at each time point.

11 Direct Access to Source Data and Documents

The Investigator(s) will permit trial-related monitoring, audits, REC review, and regulatory inspections by providing the Sponsor(s), Regulators and REC direct access to source data and other documents (e.g. patients' case sheets, blood test reports, X-ray reports, histology reports etc.).

12 Ethics & Regulatory Approvals

The trial will be conducted in compliance with the principles of the Declaration of Helsinki (1996), the principles of GCP and in accordance with all applicable regulatory requirements including but not limited to the Research Governance Framework and the Medicines for Human Use (Clinical Trial) Regulations 2004, as amended in 2006 and any subsequent amendments.

This protocol and related documents will be submitted for review to the Research Ethics Committee (REC), and to the Medicines and Healthcare products Regulatory Agency (MHRA) for Clinical Trial Authorisation.

Subsequent protocol amendments will be submitted to the REC and Regulatory Authorities for approval, and that the Chief Investigator will comply with regulations, particularly specifying, Pharmacovigilance reporting and providing the REC & MHRA with progress reports, and a copy of the Final Study Report.

The Chief Investigator will submit a final report at conclusion of the trial to the KHP-CTO (on behalf of the Sponsor), the REC and the MHRA within the timelines defined in the Regulations.

13 Quality Assurance

Monitoring of this trial will be to ensure compliance with Good Clinical Practice and scientific integrity will be managed and oversight retained, by the KHP-CTO Quality Team.

14 Data Handling

The Chief Investigator will act as custodian for the trial data. The following guidelines will be strictly adhered to:

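### Section 10 derives a trough cut-off unconditionally, and the planned association tests have no bearing on it, so no result leads to the conclusion that no predictive threshold was found

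*Combined protocol and SAP*

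**What the plan says.** The primary objective in section 4.1 is "To define a week 6 golimumab trough level concentration that predicts response at week 14". No criterion for meeting or missing it is attached.

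The opening paragraph of section 10 gives the method. With the aim "To determine a representative cut-off value for golimumab trough levels between the groups of patients stratified by disease activity/response", it says that "a receiver-operator characteristics (ROC) curve will be created". It continues: "A trade-off between sensitivity and specificity will be made to establish an adequate lower margin of the therapeutic golimumab range". It does not mention the AUC, an interval for it, a minimum value or a validation step.

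Section 10.2 adds two analyses of association. One is a comparison of groups: "Differences between responders and non-responders will be evaluated using a t-test with the threshold for statistical significance set at 0.05". The other is broader: "Univariate and bi-variate analysis will be used to assess factors predicting response, including serum golimumab levels at each time point". The t-test sentence names neither the variable nor the visit, although the same section makes drug level the main variable. Section 10.1 sizes the study at 42 per cohort with 80% power, two-sided, "to detect a mean difference" of 2 mg/L in serum concentration. It gives no standard deviation and no expected split of responders.

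**The concern.** A ROC curve almost always offers a best-looking cut-off, including when the marker carries no information. A plan that goes straight from the curve to the cut-off has to say elsewhere what evidence makes the cut-off credible, and this one does not. The t-test could be non-significant and the plan would still call for a lower bound of the treatment range.

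This matters because of how the result is meant to be used. Section 3 reports earlier week 6 thresholds of 2.5 and 2.6 µg/ml, notes that the authors of those studies asked for prospective validation, and says such data could improve the use of golimumab and inform drug-monitoring trials. A study offered in that role needs an outcome that counts as non-confirmation. The same unconditional step also serves the secondary cut-offs at weeks 6, 10 and 14 and during maintenance.

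**Working it through.** **Inputs.** From the documents: cohort 1 has 42 patients (section 4.2); two-sided test, 80% power, 2 mg/L difference (10.1); significance threshold 0.05 (10.2); cited 21-patient study with sensitivity 56%, specificity 90% and AUC 0.79 (section 3). Assumed: a maximum-Youden rule, because the trade-off is undefined; higher trough taken to favour response; and a responder split of 21/21, varied from 12/30 to 30/12. Section 3 gives about 50% primary non-response in the earlier trials.

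**The plan's own figure.** The 42 cannot be reproduced without a standard deviation, so it was solved backwards.
- If 42 is a total split 21/21: SD = 2 / [(1.960 + 0.842) × √(1/21 + 1/21)] ≈ 2.31 mg/L, or 2.26 using the t distribution. Then d = 2/2.257 = 0.886 and the binormal AUC is Φ(0.886/√2) ≈ 0.73.
- If 42 is per group: SD ≈ 3.23 mg/L (t-based), d = 0.619 and AUC ≈ 0.67. Cohort 1 would then hold only half the patients needed.

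**The ROC step when nothing is there.** J = sensitivity + specificity − 1. At 21/21 the chance that some cut-off gives J above 0 is exact: a random ordering of equal groups never rises above zero with probability 1/(21 + 1), so 1 − 1/22 = 95.5%. Simulation with trough independent of response, 10,000 runs per split:

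| Responders / non-responders | J > 0 | Median J | 95th percentile of J | J ≥ 0.30 | J ≥ 0.46 |
|---|---|---|---|---|---|
| 21/21 | 95.4% | 0.143 | 0.333 | 9.6% | 0.8% |
| 25/17 | 97.3% | 0.165 | 0.365 | 13.3% | 0.9% |
| 17/25 | 97.8% | 0.165 | 0.365 | 12.8% | 1.0% |
| 12/30 | 97.3% | 0.183 | 0.400 | 18.8% | 1.6% |
| 30/12 | 97.4% | 0.183 | 0.400 | 18.1% | 1.6% |

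Mean J is 0.17 at 21/21, 0.18 at 14/28 and 0.19 at 12/30. The benchmark of 0.46 is the cited study's 0.56 + 0.90 − 1. The 0.30 column is only a reference level and comes from neither the protocol nor the cited study.

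**What a condition would do.** Requiring a two-sided t-test p < 0.05 first would cut the share of no-association datasets yielding a cut-off to about 4.4% to 4.9%, or about 1.6% to 3.3% with responders higher. A rule that the lower limit of a 95% interval for the AUC must exceed 0.5 has a nominal error in that direction of (100 − 95)/2 = 2.5%. As a guide to scale at 21/21, the Hanley-McNeil standard error is 0.085 at an observed AUC of 0.65 (lower limit 0.483) and 0.081 at 0.70 (lower limit 0.541). The observed AUC would therefore need to lie somewhere between those two values.

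**What a condition would cost in power.** Simulated power of the DeLong lower-limit rule:

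| True AUC | 21/21 | 14/28 | 12/30 |
|---|---|---|---|
| 0.73 (the 10.1 target if 42 is split 21/21) | 81% | 76% | 72% |
| 0.79 (cited study) | 95% | 92% | 91% |

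A Mann-Whitney test at AUC 0.73 gives about 77%, 73% and 67%. The two rules disagree in about 3% to 6% of datasets at that AUC, so the plan should name one. A normal approximation to a test of the AUC at 21/21 gives 61% at a true AUC of 0.70. Power would be lower still at the 0.67 implied by the per-group reading of 10.1.

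**The case against.** The plan does test association. Section 10.2 sets up a responder comparison "with the threshold for statistical significance set at 0.05" and an analysis of predictors that includes trough at each time point, and section 10.1 sizes the study on a difference in concentration. A reader of the results would see that evidence beside any cut-off. One might therefore infer from the heading that no test is planned, or that the primary objective cannot fail. The documents support neither. Tests are planned, and a null one would presumably be reported. What is missing is any link from those tests to the cut-off, or to the week 6 and week 14 pairing.

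A reader might also infer that chance would produce a convincing threshold. The figures do not bear that out: chance reaches the cited study's J of 0.46 in about 1% to 2% of datasets, and the typical chance J is visibly poor.

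Finally, the objective is to define a level in an observational study, so estimation with honest uncertainty is a legitimate alternative to a significance gate. Section 3 also foresees later trials. This stands in part. It is a reason to build the rule on an AUC interval and to allow an exploratory cut-off, but the present plan provides neither the interval nor the label.

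**Conclusion.** The point holds in this limited form: the cut-off is unconditional, the planned tests have no stated consequence for it, and no result is designated as failure to find a predictive threshold. With no association, a cut-off better than chance on its face would appear in about 95% to 98% of datasets of 42, with J of 0.30 or more in about 10% to 19%. The risk is an unsupported and usually weak-looking threshold entering the literature, not a persuasive false one.

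The sizes rest on a maximum-Youden rule and an assumed responder split. The power figures rest also on a binormal model and, at AUC 0.73, on reading 42 as a 21/21 total. The reading of the text does not depend on any of these. This is a cheap and worthwhile improvement. It does not invalidate the study.

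**What to change.** Add to section 10, in substance:

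- The primary analysis is the AUC of the week 6 trough for response at week 14, reported with its DeLong 95% confidence interval.
- A week 6 cut-off is presented as predictive only if the lower limit exceeds 0.5. Otherwise the conclusion is that no predictive threshold was shown, and any cut-off reported is labelled exploratory.
- The same rule, labelled secondary, applies to the cut-offs at weeks 6, 10 and 14 and during maintenance.
- An AUC above 0.5 shows association only. It does not show that a particular cut-off is accurate or stable.

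Name this one rule, without leaving a choice of tests open. The change needs a few sentences and no new data. The downside is that the trial may end without a declared threshold even when a real association exists. From the power figures above, that chance is about 19% to 28% at a true AUC of 0.73 (100 − 81 and 100 − 72) and about 5% to 9% at 0.79.

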However, despite the fact that the PURSUIT trial program yielded positive results and met its primary endpoints, unanswered questions remain regarding the optimal use of golimumab in UC. For example, how could the observed rates of primary and secondary non-response (approximately 50% and 40%) be minimized? In addition to significant rates of non-response, the majority of patients who do respond to the drug remain symptomatic to some degree, are on concomitant steroids, and are without a "normal or inactive" (Mayo 0) mucosal appearance. It's possible that these outcomes could be improved upon, given a more detailed understanding of the initial exposure-response relationship data that emerged from PURSUIT.

Patients with higher serum concentrations of golimumab were observed to have higher rates of response and remission as well as greater improvement in median composite Mayo scores. In PURSUIT-SC the change from baseline Mayo score and rates of clinical response and clinical remission at week 6 increased with increasing quartiles of serum golimumab concentration. Serum quartile analysis of the subsequent maintenance trial showed that more patients in the higher quartiles achieved clinical response through to week 54, or clinical remission at both weeks 30 and 54, when compared with those in the lower quartiles.

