In a recent publication, Adedokun and colleagues reported a rigorous and meticulously performed a study of the pharmacokinetics and pharmacodynamics of golimumab using samples taken as part of the PURSUIT trials. As part of these analyses the authors found serum golimumab concentrations to be dose proportional and that a positive correlation exists between concentrations and efficacy outcomes (clinical response, clinical remission and mucosal healing) during induction and maintenance therapy. They then went further by using receiver-operating-characteristics (ROC) curve analysis to define serum golimumab concentrations that may serve as potential targets for treatment optimization; proposing thresholds of 2.5 µg/ml at week 6 and 1.4 µg/ml during steadystate maintenance therapy³. Prior to this, similar findings were also reported by a group from Leuven as part of an observational study of 21 patients being treated with golimumab in a clinical setting. Median golimumab concentrations were significantly higher in partial clinical responders than in non-responders at week 2 (10.0 vs 7.4 μ g/ml, p = 0.035) and week 6 (5.1 vs 2.1 µg/ml, p = 0.037). Their ROC curve analysis revealed a cut-off of 2.6 µg/ml at week 6 (90% specificity, 56% sensitivity, Area Under the Curve 0.79 [95% CI], p = 0.034) for the association with a partial clinical response after 14 weeks of treatment⁴. The authors of both of these studies highlighted the need for further prospective trials to validate their findings and add further validation to commercially available assays for the measurement of golimumab serum concentrations. Data such as these could be used to optimise the use of golimumab in clinical practice and inform prospective therapeutic drug monitoring trials employing trough levels to drive dosing.

Anti-drug antibodies were also detected in a small minority of patients (2.9%) in the PURSUIT trials and the majority of these (67.7%) were found to be neutralizing. Their occurrence was significantly less common in patients who were receiving concomitant

immunomodulators (1.1%) compared with patients who were not (3.8%). However, due to the low observed incidence it is difficult to draw conclusions regarding their impact on efficacy. Nonetheless, a clearer understanding of their impact on drug exposure and subsequently, disease activity would be of benefit in defining the optimal use and monitoring of golimumab.

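### The trough cut-off, the trial's primary output, is chosen by an unnamed ROC trade-off with no interval or internal validation, so its accuracy will on average be overstated

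*Combined protocol and SAP*

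**What the plan says.** Section 4.1 of the combined protocol and SAP sets the primary objective: "To define a week 6 golimumab trough level concentration that predicts response at week 14". Cohort 1 (42 patients) serves it. A secondary objective for cohort 2 (70 patients) is of the same kind: "To define a golimumab trough threshold that is associated with remission during maintenance therapy". Section 4.1 also lists, as a secondary objective, cut-offs at weeks 6, 10 and 14 for response at each of those visits.

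The method is in section 10. It says that "a receiver-operator characteristics (ROC) curve will be created" and then: "A trade-off between sensitivity and specificity will be made to establish an adequate lower margin of the therapeutic golimumab range". Section 10.2 adds descriptive statistics, univariate and bivariate analyses, and a group comparison: "Differences between responders and non-responders will be evaluated using a t-test with the threshold for statistical significance set at 0.05". None of these selects or validates a threshold.

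Sections 10 to 10.2 contain no named cut-off rule, no confidence interval for the cut-off, AUC, sensitivity or specificity, and no bootstrap, cross-validation or hold-out sample. Where section 4.1 speaks of validation, it means the assay and the patient-reported outcome, not the threshold.

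**The concern.** A cut-off chosen to look good in one small sample and then scored in that sample will, on average, look better than it performs in new patients. This is the trial's main product, and section 3 says such data could inform dosing trials driven by trough levels. Those trials need a realistic accuracy and a range for the cut-off.

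The unnamed rule adds a second problem. Different reasonable rules lead to quite different cut-offs, so a reader could not tell whether the reported value favours sensitivity or specificity. Nor could a reader tell whether a difference from the published week 6 values (2.5 and 2.6 µg/ml, section 3) reflects biology, the rule or chance. Section 3 also reports of the earlier work: "The authors of both of these studies highlighted the need for further prospective trials to validate their findings". A further cut-off scored only on its own data does not meet that need.

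**Working it through.** **The plan's own figure.** The plan states no expected AUC, accuracy or precision. Its only figure is 42 patients per cohort for a 2 mg/L mean difference (section 10.1). No SD is given, so 42 can be neither reproduced nor refuted. It follows if the SD is about 2.31 mg/L and the 42 split 21/21 (two-sided 0.05, 80% power). In either case it sizes a mean difference, not a cut-off.

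**Inputs for the illustration (assumptions, from section 3).**
- Split 21/21: primary non-response of about 50% in the earlier trial programme.
- Week 6 median troughs of 5.1 µg/ml (responders) and 2.1 µg/ml (non-responders), and AUC 0.79: the cited 21-patient study.

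**Equal-variance log-normal model.** Log SD = ln(5.1/2.1) / (√2 × Φ⁻¹(0.79)) = 0.887/1.140 = 0.778.

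The rule alone moves the target cut-off in this model:
- Youden: √(5.1 × 2.1) = 3.3 µg/ml.
- 90% sensitivity: 5.1/exp(1.2816 × 0.778) = 1.9 µg/ml.
- 90% specificity: 2.1 × exp(1.2816 × 0.778) = 5.7 µg/ml.

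At 2.6 µg/ml this model implies sensitivity 81% and specificity 61%, against the cited 56% and 90%, so it fits that point poorly.

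**Unequal-variance log-normal model.** It matches the cited 90% specificity at 2.6 µg/ml.
- Non-responder log SD = ln(2.6/2.1)/1.2816 = 0.167.
- Responder log SD, keeping AUC 0.79: √[(0.887/0.806)² − 0.167²] = 1.088.
- Sensitivity at 2.6 µg/ml is then 73%, so this model does not match the cited point fully either.

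**Simulation.** In each of 40,000 simulated trials per scenario, the cut-off was chosen by a rule and J = sensitivity + specificity − 1 was computed in the sample (apparent) and in the population at that same cut-off (true). Optimism is apparent minus true.

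| Model and split | Rule | Apparent J | True J | Optimism |
|---|---|---|---|---|
| Equal variance, 21/21 | Youden | 0.532 | 0.400 | 0.13 |
| | Closest to corner | 0.520 | 0.417 | 0.10 |
| | Specificity ≥ 90% | 0.407 | 0.346 | 0.06 |
| | Sensitivity ≥ 90% | 0.407 | 0.346 | 0.06 |
| Unequal variance, 21/21 | Youden | 0.709 | 0.649 | 0.06 |
| | Closest to corner | 0.692 | 0.624 | 0.07 |
| | Specificity ≥ 90% | 0.673 | 0.631 | 0.04 |
| | Sensitivity ≥ 90% | 0.113 | 0.062 | 0.05 |
| Equal variance, 35/35 | Youden | 0.506 | 0.407 | 0.10 |
| | Closest to corner | 0.498 | 0.422 | 0.08 |
| | Fixed 90% | about 0.37 | about 0.33 | 0.04 |

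- With Youden, equal variance and 21/21, sensitivity and specificity each appear as about 0.77 and are truly about 0.70.
- In the equal-variance 21/21 model, J is overstated in 88% of trials (Youden), 80% (closest to corner) and 67–68% (fixed 90%).
- Varying the AUC from 0.50 to 0.85 moves Youden optimism from 0.17 to 0.12. Varying the response share from 40% to 60% changes it by no more than about 0.01.
- As a control, a cut-off fixed in advance shows no bias: observed 0.717/0.715 against a true 0.716.

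**Spread of the cut-off (95% sampling range, 21/21).** Equal variance: 1.7–6.3 µg/ml (Youden) and 2.1–5.0 µg/ml (closest to corner). Unequal variance: 2.4–3.7 µg/ml (Youden).

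**Does a bootstrap correction help?** In 500 trials with 200 resamples each (equal variance, 21/21), the cut-off was re-selected in every resample.
- Youden: apparent J 0.531, corrected 0.445, true 0.400. Share of bias removed: (0.531 − 0.445)/(0.531 − 0.400) = 66%.
- Closest to corner: 0.516, 0.448, 0.417. Share removed: 0.068/0.099 = 69%.
- The bootstrap interval for the cut-off covered the best value in 93% (Youden) and 92% (closest to corner) of trials.

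**Precision to expect.** AUC 0.79 with 21/21 has a Hanley–McNeil SE of 0.071, so the 95% CI is 0.79 ± 1.96 × 0.071 = 0.65 to 0.93. Exact 95% CIs for single proportions: 17/21 gives 0.58–0.95, and 13/21 gives 0.38–0.82.

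**The case against.** The strongest reply is that the direction is safe but the size is not. The larger figures (0.13, and 1.7–6.3 µg/ml) come from the model that misses the cited operating point; the alternative roughly halves the Youden optimism and narrows the range. The 50% response share comes from another programme with another outcome definition, and the 35/35 split for cohort 2 has no source in the documents. All of this stands, so the size should be read as a range.

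Nor need both measures be inflated. If the cut-off were set from responders alone to reach 90% sensitivity, sensitivity would be overstated (0.905 against 0.863) while specificity would be essentially unbiased (0.495 against 0.494). That is correct, but such a rule is hardly a trade-off between the two, and their sum is still overstated.

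It can also be said that the study is observational, that silence on intervals does not mean none will be reported, that an independent statistician reviewed the plan, and that the rule could still be fixed before analysis. These points limit the seriousness. They do not supply the rule, the interval or the validation, because section 10 presents itself as the statistical plan and refers to no further document.

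**Conclusion.** The concern holds. As written, the plan selects its primary output by an unstated rule and evaluates it on the patients used to select it, with no measure of uncertainty. Sensitivity plus specificity was overstated on average under every rule and model tried. At 21/21 with AUC 0.79 the optimism in J is about 0.04 to 0.13, depending on rule and model; how it divides between sensitivity and specificity depends on the rule. For cohort 2, under an assumed 35/35 split and the equal-variance model, it is about 0.04 to 0.10.

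The direction does not depend on the assumed inputs; the size depends on the AUC, the distributions and, to a small degree, the response split, none of which the plan states. Optimism is an average, and any single trial may escape it. The data remain usable, so this should be corrected before analysis but does not undermine the study.

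**What to change.** Amend section 10 before analysis:

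1. Name the cut-off rule for week 6 trough against week 14 SCCAI response.
2. Report bootstrap optimism-corrected sensitivity and specificity, and a bootstrap 95% CI for the cut-off, re-selecting the cut-off in every resample.
3. Report the AUC with a 95% CI. It needs no optimism correction, since no cut-off is selected to compute it.
4. Apply the same to the cohort 2 remission cut-off and to the secondary cut-offs at weeks 6, 10 and 14.
5. As a useful addition on which items 1 to 4 do not depend, pre-specify a secondary analysis of the cited thresholds as fixed values, with exact CIs: 2.5 and 2.6 µg/ml at week 6 for week 14 SCCAI response, and 1.4 µg/ml for SCCAI remission in cohort 2. State that outcome definitions, and possibly assays, differ from the cited studies. Fixed values carry no selection bias in this sample.

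The cost is a few lines of wording and some analysis code, with no extra patients or visits. Reported accuracy will be lower and the intervals wide. At this sample size the bootstrap removes about two thirds of the optimism, not all of it, and the report should say so.
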